### 5.2 Secondary outcomes

- Time to conversion from CN to MCI Stage I (regardless of pTau217 status) and from CN to pTau217-positive status (biomarker conversion).

- Estimated ten-year conversion rates from CN to MCI Stage I, extrapolating from observed two-year data using survival/hazard modeling informed by external cohorts.
  - Hazard ratios for LOAD associated with P&R model-derived risk scores, PRS categories, and biomarker trajectories.
  - Cost per participant and per conversion event detected for different sampling strategies (fingerstick vs venous; frequency of in-person visits vs reliance on digital monitoring).
  - Incremental predictive value (AUC-ROC, net reclassification improvement) of continuous digital monitoring features (smell, location, activity, speech, EEG, sleep) beyond traditional risk factors and biomarkers.
- 

## 6. Statistical Considerations

### 6.1 General approach

Data analyses will be primarily exploratory and hypothesis-generating given the FIH nature and modest sample size, but key performance metrics (e.g., AUC-ROC) will be estimated with confidence intervals. Observational protocol templates recommend prespecifying primary analyses and sensitivity analyses for observational cohorts.

Analyses:

- Compute AUC-ROC for the P&R model and alternative models for predicting conversion to pTau217-positive MCI Stage I within 24 months.
- Compare AUC-ROC across models (proteogenomic vs proteo-methylome-genomic) using DeLong's test or similar.
- Use Cox proportional hazards models to estimate hazard ratios for time to conversion as a function of baseline P&R risk, PRS, ApoE4 dose, and biomarker levels.
- Use logistic regression and time-dependent ROC analyses for binary conversion endpoints over fixed time horizons.
- Incorporate digital monitoring variables as covariates and evaluate incremental predictive performance.
- For cost-effectiveness, compare costs and detection yield of different biospecimen and monitoring strategies using simple decision-analytic models (incremental cost per correctly predicted conversion).

Missing data will be handled using appropriate methods (e.g., multiple imputations, mixed-effects models) depending on pattern and mechanism of missingness. Sensitivity analyses will evaluate robustness of results to missing data assumptions.

---

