### Secondary aims

3. Compare the prognostic performance of the P&R model with simpler baseline models (e.g., APOE + PRS only, or clinical + cognitive only) for predicting CN  $\rightarrow$  pTau217-positive MCI conversion over 24 months.
4. Estimate, with appropriate uncertainty, short-term (2–5-year) conversion probabilities derived from the P&R model and explore how these inform projected longer-term (up to ten-year) risk in this population, recognizing that extrapolations will be preliminary and supported by external cohorts.
5. Evaluate the practical scalability and relative cost of alternative sampling and visit strategies, including venous versus capillary (fingerstick) blood collection and varying degrees of in-clinic versus remote assessment, using simple per-participant and per-conversion cost summaries.
6. Assess the incremental predictive value, beyond the core P&R model, of selected digital and wearable measures (e.g., Oura-derived sleep and activity metrics, brief speech, and digital cognitive features) for detecting CN  $\rightarrow$  MCI conversion events.

7. Determine the relationship between an Oura Ring–based exposome risk score and proteogenomic risk scores and cognitive-functional measures.

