## 2. Study Design

### 2.1 Overall design

Longitudinal retro and prospective , observational cohort study of up to 90 ApoE4-positive adults (age  $\geq 55$ ) followed for 24 months, with in-person visits every 6 months and continuous remote monitoring with Oura Ring and a subset of 10 subjects. No investigational drug or device is administered. Participants will undergo venous or capillary blood collection, CSF collection as part of this study are not performed, digital cognitive and speech biomarker assessments,( EEG, retinal imaging or MRIs may be performed outside of this study if ordered by referrals and shared by agreement with this study. Particularly in subjects that convert during this study.

Samples and data will be used to (a) apply and refine the Insilco-derived P&R model for conversion prediction, and (b) compare model-predicted risk with the study observed conversion events.

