#### **3.2 Sample size**

The initial target is ten subjects starting with subjects that have Oura Rings and then expanding to one hundred total for the full 2-year study starting in September 'twenty-six. The targeted composition is:

- CN ApoE4 carriers with a range of polygenic risk scores (PRS): Initial target of three low PRS, 3 average PRS, 4 high PRS (later expanding to 33% in each category when the enrollment expands to a total of 100 subjects)
- Participants with MCI/CDR  $< 0.5$  and pTau217-positive at baseline will not continue enrollment in the study and will be referred to a Neurologist. These numbers may be adjusted if external sponsors join the project and support expanded enrollment. The size will be adjusted with more data on the annual CN to AD-MCI conversion rates from Insilco analyses and financial feasibility of intensive longitudinal assessments.

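### The cost ratio in section 6.1 counts only true positives, so a less specific strategy can look more cost-effective without being more informative

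*Protocol*

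**What the plan says.** The protocol describes the cost work in three places.

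- Section 6.1 plans to "compare costs and detection yield of different biospecimen and monitoring strategies using simple decision-analytic models", and gives the measure in parentheses as "incremental cost per correctly predicted conversion". No other measure is named for this comparison.
- Section 5.2 lists as a secondary outcome "Cost per participant and per conversion event detected for different sampling strategies", with fingerstick versus venous sampling and in-person visits versus digital monitoring as the contrasts.
- Secondary aim 5 (section 1.2) evaluates scalability and relative cost "using simple per-participant and per-conversion cost summaries".

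Measures that respond to false positives are planned too, such as "Incremental predictive value (AUC-ROC, net reclassification improvement) of continuous digital monitoring features" in section 5.2. They serve model and feature performance and are not tied to the cost comparison. No section states a specificity, a flagged proportion or a false-positive cost for the cost comparison.

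**The concern.** A prediction strategy produces right and wrong positive calls. The section 6.1 ratio sees only the right ones. The number of converters correctly predicted can be raised by flagging more people, and the ratio attaches no price to doing so. Two strategies with the same cost and sensitivity score the same even if one raises many times more false alarms. If the less specific one is also cheaper, it always scores better.

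This matters because aim 5 asks which sampling and visit strategies are practical to scale, and the contrasts set cheaper options (fingerstick, digital monitoring) against more expensive ones. Cheaper sampling or digital monitoring could differ from the alternative in specificity, and the stated measure would not show it. A reader of the results could take a favourable ratio as evidence of efficient prediction when it partly reflects a looser cut-off.

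**Working it through.** The protocol gives no numerical result for this analysis, so there is no figure to reproduce.

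**Inputs**

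- Cohort size N: section 2.1 has "observational cohort study of up to 90 ApoE4-positive adults"; section 3.2 has "expanding to one hundred total for the full 2-year study". I use N = 90 and check 100.
- 24-month conversion proportion p: not given; section 3.2 says "The size will be adjusted with more data on the annual CN to AD-MCI conversion rates from Insilco analyses". Assumed 10%, with 5% and 20% as a range.
- Sensitivity (se), specificity (sp) and cost per participant (c): not given, so assumed. One unit is the testing cost of one participant under the dearer strategy.

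**Formulas**

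Converters D = N × p. True positives TP = se × D. False positives FP = (1 − sp) × (N − D). Cost per true positive = N × c / (se × D). Specificity does not appear in the last expression. The incremental form, difference in cost over difference in TP, does not contain it either.

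**1. Same cost and sensitivity, falling specificity**

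N = 90, D = 9, c = 1, se = 0.8, so TP = 7.2 and cost per TP = 90 / 7.2 = 12.5. The last column adds an assumed charge of one unit per positive call: (90 + TP + FP) / 7.2.

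| sp | FP = 81 × (1 − sp) | FP per TP | Cost per TP | Cost per TP with charge |
|---|---|---|---|---|
| 0.95 | 4.05 | 0.56 | 12.5 | 14.1 |
| 0.8 | 16.2 | 2.25 | 12.5 | 15.75 |
| 0.5 | 40.5 | 5.6 | 12.5 | 19.1 |
| 0.2 | 64.8 | 9.0 | 12.5 | 22.5 |
| 0 | 81 | 11.25 | 12.5 | 24.75 |

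At sp = 0.2 the strategy flags 80% of converters and 80% of non-converters, so it carries no information, yet it ties with the strategy at sp = 0.95. The row at sp = 0 is a limiting case.

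**2. A looser cut-off at equal cost**

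Moving from se 0.8 to se 0.9 gives TP = 8.1 and cost per TP = 90 / 8.1 = 11.1, against 12.5. This holds at any specificity, including sp = 0.1, where the rule is uninformative and FP = 81 × 0.9 = 72.9 against 16.2 for se/sp 0.8/0.8.

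**3. A cheaper, less specific strategy**

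With c = 0.2, se = 0.8 and sp = 0.3, total cost is 18, cost per TP is 18 / 7.2 = 2.5 and FP = 56.7. The dearer strategy (c = 1, se/sp 0.8/0.8) has 12.5 and 16.2. The cheaper one saves 72 units for the same TP, so it wins on the stated ratio. With a charge w per positive call, total costs are 18 + 63.9w and 90 + 23.4w. They are equal at w = 72 / 40.5 = 1.8. Above that charge the order reverses, so the false-alarm cost decides the comparison.

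**4. Range**

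At N = 90 and se = 0.8, cost per TP is 90 / 3.6 = 25 for p = 5% and 90 / 14.4 = 6.25 for p = 20%. For N = 100 and p = 10% it is 100 / 8 = 12.5. In every case it is unchanged by specificity.

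**The case against.** Four counter-arguments carry weight.

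- **The other two cost measures are different.** Section 5.1 defines conversion by consensus diagnostic criteria plus plasma pTau217 above a cut-off. A conversion event in section 5.2 or aim 5 is therefore a diagnosis and cannot be obtained by flagging more people. A reader might infer that all three places share the defect; the text does not support that. This stands.
- **A decision-analytic model can carry false-alarm costs.** Section 4.3 attaches a targeted evaluation to a suspected decline, and nothing excludes that cost from the numerator. Cost components may also be set out in an analysis plan that is not at hand. This stands in part: it rules out saying that false positives are certain to be ignored. It does not rescue the ratio that the protocol itself names, which has no such term unless one is added.
- **The P&R cut-offs are not free.** Section 2.2 locks the model and derives its risk thresholds beforehand from external cohorts, so they are not loosened strategy by strategy. However, it does not say which level counts as a predicted conversion, and no cut-off is given for monitoring strategies.
- **Little rests on it.** Section 6.1 says the strategies are compared, not ranked, no selection follows, and the analyses are called primarily exploratory. This stands and limits the weight of the point.

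**Conclusion.** The point holds for section 6.1 only. The named ratio is insensitive to specificity, and no common operating point or false-positive charge is stated. That result is algebraic. The illustrative sizes (12.5 units per true positive with anything from 4 to 81 false positives) rest on assumed N, conversion proportion, sensitivity and unit costs.

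Two stronger readings are tempting and should not be adopted. One is that calling everyone a converter without a test beats every real strategy. That follows only if cost means assay and device cost alone, and flagging everyone is not among the strategies to be compared. The other is that the ratio will usually favour an uninformative rule. In simulation with an assumed 10 converters in 100 and a score of AUC 0.80 flagging 25 people, a random rule flagging 75 finds more converters in 62% of studies. At 50 flagged the figure is 17%, and at the same 25 about 1%. The result comes from unequal flagging, which is why matching the flagged proportion is the remedy.

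This is a minor point and a cheap improvement. The analysis is secondary and exploratory, and the primary AUC analysis is unaffected.

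**What to change.** Change section 6.1 only:

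- Compare strategies at the same specificity or the same flagged proportion.
- Report false positives per true positive beside the cost ratio.
- State that the cost of evaluations triggered by false alarms is counted.

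Alternatively, report net benefit at a stated risk threshold, with flag-all and flag-none as reference strategies.

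Sections 5.2 and aim 5 need at most a wording check so that detected and predicted conversions are kept apart. The cost is a few sentences and a little more analysis on data already collected. The downside is that the cost ratios will look less favourable once false alarms are counted.

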## **7. Data Management and Confidentiality**

### **7.1 Data collection and storage**

- Data will be collected in a secure, 21 CFR Part 11-capable electronic data capture system (e.g., REDCap or equivalent).
- Each participant will be assigned a unique study ID; direct identifiers will be stored separately in a secure linkage file.
- Digital device data (location, activity, speech metrics, sleep) will be transmitted via encrypted channels and stored on secure servers with role-based access controls.
- Access to identifiable data will be limited to authorized study personnel; analysts will work primarily with coded datasets.

### **7.2 Confidentiality protections**

- All study staff will complete human subjects and HIPAA training.
  - Any reports or publications will present aggregated or de-identified data only.
  - Data sharing with collaborators and sponsors will occur in de-identified form under data use agreements consistent with IRB and institutional policies.
- 

## **8. Risks and Benefits**

### **8.1 Risks**

- Venipuncture and fingerstick: transient discomfort, bruising, rarely infection or vasovagal reactions.
- Lumbar puncture (if clinically indicated): headache, back pain, very rarely bleeding or infection.
- EEG and retinal imaging: minimal risk, possible mild discomfort, or fatigue from procedures.

- Amyloid PET scans (if clinically indicated): radiation exposure within clinical standards, potential anxiety about results.
- Digital monitoring: privacy concerns such as information on location, activity, and speech data collection; risk of data breach if security were compromised.
- Psychological risks: anxiety, distress, or altered self-image related to information about genetic risk, biomarker status, and early cognitive changes.

These risks are typical of observational Alzheimer's biomarker studies and continuous monitoring protocols when appropriate safeguards are applied.

## 8.2 Risk mitigation

- Use trained personnel and SOPs for venipuncture and lumbar puncture; monitor for adverse events.
- Use minimal necessary imaging and adhere to clinical indications and radiation safety guidelines.
- Apply robust cybersecurity measures, encryption, and strict access controls for digital data.
- Provide pre- and post-test counseling for genetic and biomarker information as appropriate; offer referrals to counseling services.
- Allow participants to opt out of specific optional components (e.g., CSF, certain digital features) while remaining in other parts of the study when feasible.

## 8.3 Potential benefits

- Participants may gain early insights into cognitive status and risk factors, which may inform future clinical decision-making though direct clinical benefit is not guaranteed.
  - Society may benefit from improved models for early detection and staging of AD, more scalable biomarker strategies, and evaluation of continuous monitoring for CN → MCI transitions.
- 

## 9. Informed Consent Process

- Informed consent will be obtained by qualified study personnel in a secluded setting before any study-specific procedures.
- The consent process will explain:
  - Study purpose, procedures, duration, and follow-up.
  - Risks and benefits.

- Alternatives (non-participation, standard clinical care).
- Confidentiality protections and data sharing plans.
- Voluntary nature of participation and right to withdraw at any time without affecting clinical care.
- Handling and potential disclosure of genetic and biomarker results (including whether individual results will be returned and under what conditions).
- For digital monitoring, consent will explicitly address what types of data are collected (e.g., GPS, accelerometry, speech features not content), how they are used, and participants' options to pause or discontinue monitoring.

Consent documents will follow institutional templates for observational studies and genetic/biomarker research.

---

## 10. Safety Monitoring and Reporting

- The principal investigator (PI) will oversee ongoing safety monitoring.
  - Given the minimal-to-moderate risk and observational nature, a formal external Data Safety Monitoring Board is not initially planned but may be added if required by the IRB or sponsors.
  - Unanticipated problems involving risk to participants or others and serious adverse events (SAEs) related to study procedures (e.g., complications from lumbar puncture) will be reported to the IRB per institutional policy.
  - Annual continuing review reports will summarize enrollment, retention, adverse events, and protocol deviations.
- 

## 11. Privacy, HIPAA, and Data Sharing

- This study involves collection of protected health information (PHI); a HIPAA authorization will be incorporated into the consent, or a waiver will be sought as appropriate.
- PHI will be limited to the minimum necessary.
- Data sharing with external collaborators and potential industry sponsors will use de-identified or limited datasets under data use agreements that prohibit attempts at re-identification and require appropriate safeguards.
- Any future use of stored biospecimens and data beyond the current protocol will require either explicit participant consent or appropriate IRB/HIPAA determinations.

---

## 12. Vulnerable Populations and Special Considerations

- The study does not specifically target children, prisoners, or pregnant individuals; these populations will be excluded.
  - Older adults with subtle cognitive changes are included; consent capacity will be formally assessed when there is concern, and legally authorized representatives may be involved if institutional policy allows and the IRB approves this approach.
- 

## 13. Dissemination of Results

- Findings will be disseminated via peer-reviewed publications and conference presentations.
- Results will be reported in aggregate; any case-level descriptions will be de-identified.
- Participants will be offered a lay-language summary of overall study findings at study completion if desired.

## 15. Abbreviations

**A $\beta$ 42/40:** Amyloid-beta 42/40 ratio

**AD:** Alzheimer's Disease

**AD-MCI:** Alzheimer's Disease- MCI

**APOE:** Apolipoprotein E

**AUC-ROC:** Area Under the Curve-Receiver Operating Characteristic

**AUCs:** Areas Under the Curve

**CBC:** Complete Blood Count

**CDR:** Clinical Dementia Rating

**CMP:** Comprehensive Metabolic Panel

**CN:** Cognitively Normal

**CSF:** Cerebrospinal Fluid

**EEG:** Electroencephalogram

**EMR:** Electronical Medical Record

**GFAP:** Glial Fibrillary Acidic Protein

**GPS:** Global Positioning System

**GWAS:** Genome Wide Association Studies

**HIPAA:** Health Insurance Portability and Accountability Act

**HR:** Hazard Ratio

**IRB:** Institutional Review Board

**LOAD:** Late Onset Alzheimer's Disease

**MCI:** Mild Cognitive Impairment

**mDNA:** methylated Deoxyribonucleic Acid

**MRI:** Magnetic Resonance Imaging

**NfL:** Neurofilament Light

**PET:** Positron Emission Tomography

**PI:** Principal Investigator

**P & R:** Progression and Risk

**PHI:** Personal Health Information

**PRS:** Polygenic Risk Score

**pTau217:** phosphorylated Tau 217

**REDCap:** Research Electronic Data Capture

**SAE:** Serious Adverse Events

**SOPs:** Standard Operating Procedures

**SCD:** Subjective Cognitive Decline

**SNP:** Single Nucleotide Polymorphism

**WCG:** WCG Institutional Review Board

**WGS:** Whole Genome Sequencing
